Exploratory efficacy endpoints	
Use of migraine medications
 
Treatment patterns of Nerivio use as a standalone treatment vs. in combination with medications were extracted from the 2-hours post-treatment reports, as the percentage of treatments in which no rescue headache medications were used (Nerivio standalone), or Nerivio was used with over-the-counter (OTC) medications, or with prescription medications (Rx).
 
Nerivio treatment stimulation intensity
 
Treatment intensity (stimulation current) is set by patients via the smartphone app and automatically recorded. The average intensity over all treatments per patient was calculated to provide personal intensity levels, which was used for the analyses. Average personal intensity levels and the range for 80% of the users were calculated over the patient cohort.
 
Nerivio utilization
 
Average (and/or median) of number of Nerivio treatments per month. A specific cohort of this outcome considers safety in patients who use the device at high frequency, close to the every-other-day regime of preventive treatment.

Datasets	
1. Intent to treat analysis set (ITT) The ITT analysis set includes all users who had at least one treatment2. Modified intent to treat analysis set (mITT) The mITT analysis set includes all ITT participants who had at least 2 treatments with prospective electronic diary reports at the beginning of the treatment ("baseline") and 2 hours post the beginning of the treatment.
Data Analysis	The ITT analysis set was used for the safety assessments and the mITT analysis set was used for the efficacy assessments.

STATISTICAL CONSIDERATIONS FOR RWE-009 STUDY

The study hypothesis was that treatments of migraine with the Nerivio device in children will be as safe and effective as previously described in adolescents and adults.

DATA COLLECTION

BASELINE DATA

Baseline participant characteristics (age, gender) were collected from the Nerivio account of each participant.

TREATMENT DATA

Treatment data was retrieved from the Nerivio app for each treatment. Data includes automatic parameters (e.g time of treatment, location, device serial number, treatment intensity etc...) and individual information completed by the participant (pain level before and after the treatments, migraine symptoms, functional disability before and after the treatment etc...)

COMPUTER SOFTWARE

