All statistical analyses and data presentations, including tabulations and listings, were performed using the SAS version 9.4 software.

STATISTICAL ANALYSIS

Demographic and Baseline Analysis

Demographic and baseline condition related characteristics will be tabulated and compared between the participant age data type. Continuous variables will be summarized by a mean, standard deviation, minimum, median and maximum and categorical variables by a count and percentage.

Safety Endpoints Analysis

The rate of device related adverse event (DRAE) was calculated ad the number of reported DRAE divided by the number of participants in the study.

Efficacy Endpoints Analysis

All the endpoints will be calculated for Qualified Attacks only, Qualifies treatement was defined as

- 1 - Attacks treated with Nerivio for at least 30 minutes
- 2 – Pre and post treatment data was reported by the participant for the specific treatment
- 3 – No rescue medications were taken before and during the 2 hours post treatment, according to the participant report

Consistent efficacy was conducted in cases where at least two qualified treatments were performed. Patients who experienced the outcome (e.g., pain freedom) in at least 50% of their reported treatments, during which they did not report the use of rescue medications, were considered responders.

Headache pain and functional disability were rated at baseline and at 2 h post-treatment on a 4-point scale: severe, moderate, mild, or none. Migraine associated symptoms (photophobia, phonophobia, and nausea/vomiting) were marked as present or not.

Pain relief was calculated as a decrease from severe or moderate levels at baseline to mild or none at 2 h posttreatment.

Functional disability relief was calculated as any improvement in disability from baseline to 2 h posttreatment.

Pain/functional disability freedom was calculated as a decrease from any pain/disability level at baseline to none at 2 h post-treatment.

Freedom from a specific migraine-associated symptom was calculated as the percentage of patients reporting the presence of that symptom at baseline and the lack of that symptom at 2 h post-treatment. Freedom from at least one associated symptom was calculated as the percentage of patients in which one or more associated symptom(s) were reported at baseline and the lack of at least one of those symptoms at 2 h post-treatment.

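### The rescue-free qualified-treatment rule is not limited to the 2-hour response endpoints, so as written it fixes medication use at 100% standalone and can only lower the treatment count

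*Combined protocol and SAP*

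**What the plan says.** In the SAP part, under Efficacy Endpoints Analysis, the scope is stated without exception: "All the endpoints will be calculated for Qualified Attacks only". Three conditions define a qualified treatment:

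1. Duration: the session lasted half an hour or longer.
2. Reporting: the child's diary holds an entry both ahead of that session and after it.
3. Rescue-free status: "No rescue medications were taken before and during the 2 hours post treatment, according to the participant report"

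The protocol table has a row headed "Exploratory efficacy endpoints" with three entries:

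- **Medication use.** It is taken from the reports made two hours after treatment. It comprises "the percentage of treatments in which no rescue headache medications were used", which is the standalone category, alongside categories for use with over-the-counter (OTC) and prescription (Rx) medication.
- **Stimulation intensity.** It is recorded automatically and averaged across every treatment of each patient.
- **Utilization.** It is defined as "Average (and/or median) of number of Nerivio treatments per month". The same entry mentions a cohort for looking at safety in children whose use approaches an alternate-day pattern.

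Two other rows matter. The Exclusion Criteria row removes treatments of less than 30 minutes. The Datasets and Data Analysis rows assign efficacy to the mITT set (at least two treatments with baseline and 2-hour reports) and safety to the ITT set. Neither set has a rescue-free condition.

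**The concern.** The exploratory measures carry the label of efficacy endpoints, and the efficacy section filters all endpoints without exempting any. The filter conditions on the absence of rescue medication, which is the very quantity the medication-use endpoint is meant to measure. An endpoint restricted in this way has only one possible answer.

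A 100% standalone figure in a paediatric report could be taken as a finding about the need for medication, when it would only restate the filter. Utilization has a related problem. A measure of how often children use the device should not depend on whether they completed a diary or took a tablet. If the filtered count were also used to pick out high-frequency users, children with heavy exposure but incomplete diaries, or with concurrent medication, could be missed from that safety look.

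**Working it through.** The plan gives no figure to reproduce for these endpoints. The check is set logic, followed by an illustration with assumed inputs.

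**Medication use.** Let Q be the treatments that meet all three conditions. Condition 3 requires no rescue medication, and the standalone category is defined by no rescue medication. Provided both draw on the same participant report,

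P(standalone | Q) = P(no rescue | at least 30 min, both reports, no rescue) = 1.

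The OTC and Rx categories are therefore empty. Suppose the true standalone share among 1,000 reported treatments is 30, 50, 70 or 90%. The filter keeps 300, 500, 700 or 900 treatments, all of them standalone, so the reported share is 300/300, 500/500, 700/700 or 900/900. It is 100% each time. With condition 3 removed, the same data return 30, 50, 70 and 90%.

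**Utilization.** Let T be a child's treatments per month of at least 30 minutes, r the share of these with both reports, and s the rescue-free share of the reported ones. Then

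counted treatments per month = T × r × s.

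The Exclusion Criteria row already removes treatments under 30 minutes, so the additional loss comes only from conditions 2 and 3. The documents give none of T, r and s. The values below are assumptions, with T = 15 standing for roughly every-other-day use (30/2).

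| r | s | counted fraction r × s | counted per month at T = 15 |
|---|---|---|---|
| 0.3 | 0.5 | 0.15 | 2.25 |
| 0.3 | 0.9 | 0.27 | 4.05 |
| 0.6 | 0.7 | 0.42 | 6.3 |
| 1.0 | 0.5 | 0.50 | 7.5 |
| 1.0 | 0.9 | 0.90 | 13.5 |

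The count equals T only when r = s = 1. Otherwise it is too low. The direction is certain and the size is not.

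**Intensity.** No arithmetic is needed. The protocol row averages across all of a patient's treatments, whereas the SAP sentence would average over Q only. Both cannot hold unless every treatment qualifies.

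**The case against.** The strongest reply is that the filter was never meant for these measures. The OTC and Rx categories make sense only without it, and the intensity entry already says that all treatments are used. Every outcome defined after the filter in the Efficacy Endpoints Analysis section is a 2-hour response in pain, disability or associated symptoms, or the 50% responder rule. Medication use, intensity and utilization do not appear there. This is probably the intended reading. It does not remove the problem, because it concedes that the two parts of the document disagree and that a scoping sentence is missing. The mITT definition does not settle it either: it selects children, whereas the filter selects treatments.

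Three stronger inferences are tempting but unsupported:

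- A reader might infer that the study did report 100% standalone use. The documents show only what the rule implies. The exploratory row describes the extraction in the past tense and does not say that the filter was used.
- A reader might infer that the high-frequency safety cohort is misclassified. That follows only if the cohort is built from the filtered count. The document gives no numerical cut-off for the cohort, and safety is assigned to the ITT set, which has no diary or rescue condition.
- A reader might attach a particular percentage to the utilization undercount. No such figure can be derived from the documents.

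It is also fair to say that these endpoints are exploratory and descriptive. This point leaves the primary safety endpoint and the secondary 2-hour endpoints untouched.

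**Conclusion.** The concern holds as a contradiction between the SAP's filter and the protocol's exploratory endpoints. It is a rule that gives a wrong result if followed, and not merely a missing detail. For medication use the consequence is exact: 100% standalone, 0% OTC and 0% Rx. This needs no assumption about the data beyond a shared definition and report of rescue medication. For utilization the bias can only be downward, by a factor r × s that the documents do not supply. For intensity the two statements conflict directly, and the protocol wording is the one suited to an automatically recorded quantity. Any effect on the high-frequency safety cohort is conditional on how that cohort is defined. Correction is worthwhile, and its importance is limited by the exploratory status of the endpoints.

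**What to change.** State in the Efficacy Endpoints Analysis section that the qualified-treatment rule applies only to the 2-hour pain, associated-symptom and functional-disability endpoints. Then give the exploratory endpoints their own denominators:

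- **Medication use:** all treatments with a 2-hour medication report, together with the number of treatments that lack one.
- **Utilization:** all device-recorded treatments, regardless of diary completion or rescue use. If the high-frequency cohort is defined from utilization, say that this count is the one used.
- **Intensity:** the same treatments, as the protocol row already provides.

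Counting all device-recorded treatments collides with the Exclusion Criteria row, so the text must also say whether treatments shorter than 30 minutes enter utilization and intensity.

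The cost is one scoping sentence, short denominator definitions and a decision on the 30-minute question. The data sources already described in the document supply what is needed, so no new collection is required. If the analyses have been run, the sponsor should state which denominators were used and rerun any exploratory table to which the filter was applied.

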Primary endpoint - Safety	Rate of Device Related Adverse Events Incidence of device-related adverse events (DRAEs) reported by subjects. a) Percentage of patients reporting DRAEs b) Severity of reported DRAEs

Secondary endpoints - efficacy	
Consistent Headache Relief at 2 Hours Post-treatment.
 
The proportion of subjects reporting headache relief at 2 hours post-treatment in at least 50% of all their treatments.
 
Consistent Freedom from Headache at 2 Hours Post-treatment.
 
The proportion of subjects reporting freedom from headache at 2 hours post-treatment in at least 50% of all their treatments.
 
Freedom from a specific migraine associated symptom.
 
Freedom from a specific migraine associated symptom was calculated as the percent of patients reporting the presence of that symptom at baseline, and the lack of that symptom at 2-hours post-treatment in at least 50% of all their treatments.
 
Per the ICHD-3, migraine associated symptoms are:
 
a) Hyper sensitivity to light (phonophobia)b) Hyper sensitivity to sound (phonophobia)c) Nausea (with or without vomiting) 
Functional disability relief
 
Functional disability relief was calculated as decrease of at least one level of functional disability from baseline to 2-hours post-treatment in at least 50% of all their treatments.
 
Disability levels are (0) none (full function), (1) mild disability, (2) moderate disability, and (3) severe disability.
 
Freedom from functional disability
 
Freedom from functional disability was calculated as decrease from any disability level (3, 2, or 1) at baseline to no disability (i.e., return to full function) at 2-hours post-treatment in at least 50% of all their treatments.

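### The efficacy responder endpoints are defined on different treatments and different children in different sections, and no planned analysis shows what leaving out medicated treatments does to the rates

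*Combined protocol and SAP*

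**What the plan says.** Three parts of the combined protocol and SAP define who and what is counted.

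- **RWE-009 Study Protocol, Secondary endpoints.** Headache relief is "The proportion of subjects reporting headache relief at 2 hours post-treatment in at least 50% of all their treatments". The other secondary responder endpoints use the same denominator. None carries a medication condition.
- **RWE-009 Study Protocol, Datasets and Data Analysis.** "The mITT analysis set includes all ITT participants who had at least 2 treatments with prospective electronic diary reports" at baseline and at 2 hours, and "the mITT analysis set was used for the efficacy assessments". Again there is no medication condition.
- **Statistical Analysis, Efficacy Endpoints Analysis.** "All the endpoints will be calculated for Qualified Attacks only". A qualified treatment lasts at least 30 minutes, has pre- and post-treatment data, and meets criterion 3: "No rescue medications were taken before and during the 2 hours post treatment, according to the participant report". Then: "Consistent efficacy was conducted in cases where at least two qualified treatments were performed". A responder is a child with the outcome "in at least 50% of their reported treatments, during which they did not report the use of rescue medications, were considered responders".

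The only planned output on medication is in the Exploratory efficacy endpoints row: the percentage of treatments used standalone, with over-the-counter drugs, or with prescription drugs. It is not linked to outcome.

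**The concern.** The study hypothesis (Statistical Considerations) is that the device is as safe and effective in children as already described in adolescents and adults. In a single-arm study the efficacy half rests on these responder rates, so the reader must know which treatments and which children a rate describes. As written, that depends on the section consulted.

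Criterion 3 also combines two different things. Medication taken before the treatment is a co-treatment. Medication taken between the start and 2 hours may be a consequence of the device not working. Where it is, removing the treatment removes a failure from the child's denominator and can raise the responder rate relative to counting it as a failure. Nothing planned shows by how much, and nothing reports how many treatments or children each endpoint loses.

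These are secondary endpoints. The primary safety endpoint uses the ITT set and is not affected.

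**Working it through.** The plan states no rescue rate, expected responder rate, margin or numerical sample size, so there is no figure of its own to reproduce.

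**1. Definitions side by side.**

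| Source | Treatments in the 50% rule | Children |
|---|---|---|
| Secondary endpoints | all of the child's treatments | not restricted there |
| Datasets / Data Analysis | not stated | at least 2 treatments with paired reports |
| Efficacy Endpoints Analysis | at least 30 minutes, paired reports, no rescue medication | at least 2 such treatments |

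The 30-minute limit is already in the Exclusion Criteria and the paired-report condition is already in the mITT definition. The unmatched parts are criterion 3 and the minimum of two qualified treatments.

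**2. Two children** (all treatments at least 30 minutes with paired reports).

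- Child A: 2 unmedicated successes, 4 medicated failures. Qualified treatments: 2/2 = 100%, responder. All treatments: 2/6 = 33%, non-responder.
- Child B: 1 unmedicated success, 1 medicated failure. All treatments: 1/2 = 50%, a responder and in the mITT set. Only 1 qualified treatment, so not analysed.

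Both the denominator and the set of children differ.

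**3. Direction.** Let a child have K paired-report treatments, q of them unmedicated, with s unmedicated successes. Since q ≤ K, s/q ≥ s/K. For any analysed child, the qualified-treatment share is never below the share with medicated treatments counted as non-response. Against outcomes taken as observed regardless of medication, no such ordering holds.

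**4. Illustrative size (all inputs assumed).** 500,000 simulated children per case; per-treatment success without added medication drawn from Beta(0.8, 1.2), mean 40%; 2 to 10 treatments per child, uniform; responder = success in at least 50%; Monte Carlo error about 0.1 point. The bound counts every medicated treatment as non-response in all mITT children. The device-alone rate is 42.5% throughout; brackets show points from it.

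| Medication taken in | Qualified rule | Bound | mITT children dropped |
|---|---|---|---|
| 20% of failures only | 48.2% (+5.7) | 42.5% (0) | 3.1% |
| 40% of failures only | 56.1% (+13.6) | 42.5% (0) | 7.7% |
| 60% of failures only | 67.1% (+24.6) | 42.5% (0) | 14.9% |
| 12% of all treatments, unrelated to response | 42.9% (+0.4) | 37.1% (−5.4) | 3.0% |
| 24%, unrelated | 43.5% (+1.0) | 30.7% (−11.8) | 7.0% |
| 36%, unrelated | 44.3% (+1.8) | 23.6% (−18.9) | 12.5% |
| 40% of failures, 20% of successes | 51.1% (+8.6) | 32.9% (−9.6) | 10.7% |

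Rows 1 to 3 and rows 4 to 6 have the same overall medication use (for example 20% × 60% failures = 12%). What differs is only why the medication was taken.

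Variants with rescue in 40% of failures:

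- Adding medication before 10% of treatments: qualified rule 56.7%. Counting only medication after the start as failure, and leaving out treatments with medication only beforehand, gives 41.7%; the untimed bound gives 38.0%.
- Endpoint's baseline condition met in 70% of treatments: 58.3% against 43.8%. The bound here covers children with at least two baseline-eligible treatments, about 90% of the mITT. The rule drops 11.9% of those, or about 20% of all mITT children lack two qualifying treatments.
- All treatments as observed: 42.5%, 57.2% or 75.8% if 0%, 50% or 100% of rescued failures report relief, against 56.1% under the qualified rule. The shift can go either way.

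**5. Exact check under different assumptions.** K = 4, success 0.40, 10% of successes medicated, a share f of failures medicated. Unmedicated success has probability 0.40 × 0.90 = 0.36.

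- Bound: 1 − 0.64⁴ − 4 × 0.36 × 0.64³ = 1 − 0.168 − 0.377 = 45.5%, whatever f is.
- Qualified rule: for n qualified treatments each succeeds with probability 0.36/(0.36 + 0.60(1 − f)). Averaging P(at least n/2 successes) over n = 2, 3, 4 gives 56.3%, 68.5% and 83.1% for f = 30%, 50% and 70%.
- Gaps: 10.8, 23.0 and 37.6 points. Share of children with two qualified treatments: 96%, 88% and 75%.

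**The case against.** The strongest reply is that Efficacy Endpoints Analysis is the detailed section and simply makes the protocol table operational. The endpoint wording cannot be literal anyway, since short treatments are excluded elsewhere and an outcome cannot be scored without paired reports. The children analysed are a subset of the mITT set, not another population. Efficacy of the device used alone is a legitimate target, criterion 3 is stated openly, and overall medication use will be reported. Counting rescue as failure is a choice of estimand, and without medication times it may mislead.

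Much of this stands. Standalone use is a coherent target, and the rule may remain the main analysis. The responder sentence read alone could mean success without rescue among all reported treatments, which in the 40%-of-failures case gives 44.5% rather than 56.1% in the same retained children. That reading is weak, because the section opens by limiting every endpoint to qualified treatments. The failure-only gaps also mix two effects: in the same retained children they are 5.1, 11.6 and 19.7 points (48.2 − 43.1, 56.1 − 44.5, 67.1 − 47.4), not 5.7, 13.6 and 24.6. The assumed rates are not evidence about this trial.

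It does not remove the point. The endpoint row does not refer to qualified treatments, the mITT set still admits children whom the analysis section drops, the endpoints are not labelled as standalone use, and a descriptive percentage of medicated treatments cannot show the effect on any endpoint.

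**Conclusion.** The concern holds and should be fixed. The definitions conflict on their face, and no planned analysis shows the effect of leaving out medicated treatments. Confidence is high on those two statements only.

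The size is unknown because the documents give no rescue rate. Under the assumed inputs of the simulation, the qualified rule lies from about 0.4 to 25 points above the device-alone rate, and the bound from 0 to 19 points below it, according to whether medication marks failure or planned combination use. Neither figure alone settles the matter, which is why both should be shown. The documents also do not say how medication was handled in the earlier adolescent and adult data, so comparability with those rates cannot be judged from them.

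**What to change.** 1. Reconcile the Secondary endpoints, Datasets and Efficacy Endpoints Analysis text to one denominator and one analysis set, and reword the responder sentence so that it has one reading. If the qualified-treatment rule stays as the main analysis, label it standalone-use efficacy in children with at least two unmedicated treatments.
2. For each endpoint, report how many treatments and how many children criterion 3 removes.
3. Add a sensitivity analysis in mITT children with at least two treatments that last at least 30 minutes, have paired reports and meet the endpoint's baseline condition. Count medication between treatment start and 2 hours as non-response; leave out treatments with medication only beforehand. If the diary cannot separate timing, count all medicated treatments as non-response and present the result as a conservative bound beside the main result, not in its place.
4. Wherever rates are compared with adolescents and adults, state how medication was handled in those data, or that this is unknown.
5. The last treatment was in October 2023; label the addition post hoc if results are already known.

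The cost is SAP wording and a re-run on data already in the 2-hour report. No medication time stamp is described, so the untimed bound may be the only version possible. Its drawback is that it understates the device where medication was planned combination use, by about 5 to 19 points in the unrelated-use cases above, so the label matters. Only analysis and wording change.

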1 TITLE PAGE

Study title: A prospective, single arm, open label post market study assessing the safety and efficacy of Nerivio for the treatment of migraine in children under the age of 12

Test Device: Nerivio

Indication studied: Acute treatment of migraine

Study description: Prospective, single arm, open label post market study

Sponsors: Theranica Bioelectronics Ltd

Protocol: RWE-009

Clinical Phase: Post market study

Study period: First user first treatment - May 2020
Last user last treatment - October 2023

Investigators: [name] [name]

Statistician: [name].
Koren Statistics
[name]

2 RWE-009 Study Protocol

Title	A prospective, single arm, open label post market study assessing the safety and efficacy of Nerivio for the treatment of migraine in children under the age of 12
Investigational Device	Nerivio is an FDA-approved remote electrical neuromodulation (REN) device for the acute and/or preventive treatment of migraine with or without aura in patients 12 years of age or older. Nerivio delivers transcutaneous electrical stimulation to the upper arm to induce conditioned pain modulation (CPM) that activates a descending endogenous analgesic mechanism. The treatment is self-administered and controlled by a smartphone application.
Objectives	The study assessed the safety and efficacy of Nerivio for acute treatment of migraine in children under the age of 12.
Participant Population	Children who were prescribed with the Nerivio device for the treatment of migraine and were under the age of 12.
Sample size	The sample size was defined as all Nerivio users in the Nerivio database under the age of 12 in the day of their first treatment
Inclusion Criteria	
• Prescribed with Nerivio device for the treatment of migraine• Age under 12 at their first Nerivio treatment• Treat with Nerivio at least once
Exclusion Criteria	
• Treatments shorter than 30 minutes
Study Design	A prospective, data analysis of users that met the inclusion criteria was performed. All data that were reported prior and following the treatments by the users using the electronic diary within the Nerivio application were downloaded from Theranica server in an unidentified manner.

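### Pain freedom counts mild-start treatments but pain relief cannot, so freedom is not nested in relief and both rates depend on an unreported baseline severity mix

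*Combined protocol and SAP*

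**What the plan says.** Under Efficacy Endpoints Analysis in the statistical section, the scale is set out first: "Headache pain and functional disability were rated at baseline and at 2 h post-treatment on a 4-point scale: severe, moderate, mild, or none". Relief is limited to the two upper starting levels: "Pain relief was calculated as a decrease from severe or moderate levels at baseline to mild or none at 2 h posttreatment". Freedom is not: "Pain/functional disability freedom was calculated as a decrease from any pain/disability level at baseline to none at 2 h post-treatment". The disability counterpart in the synopsis shows that mild is meant to be included, since it spells out a "decrease from any disability level (3, 2, or 1) at baseline to no disability".

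A treatment qualifies on three conditions: its duration, no rescue medication, and available data ("Pre and post treatment data was reported by the participant for the specific treatment"). None of them refers to how severe the pain was at the start. A child is a responder on an outcome if it occurred in half or more of the child's reported treatments without rescue medication, given at least two qualified treatments. No separate denominator is given for relief.

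The synopsis, under Secondary endpoints - efficacy, gives no baseline condition for either pain endpoint. Freedom there is "The proportion of subjects reporting freedom from headache at 2 hours post-treatment in at least 50% of all their treatments", and relief is "The proportion of subjects reporting headache relief at 2 hours post-treatment in at least 50% of all their treatments".

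**The concern.** Readers expect freedom to be the stricter form of relief, so that every treatment ending pain-free is also a relief. Here that fails. A child who treats only mild headaches, all of which clear, is a consistent freedom responder and can never be a relief responder.

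The study has one arm, and its stated hypothesis is that the device works as well in children as previously described in adolescents and adults. Without a control group, a difference in how early or how mild the headaches were when treated cannot be separated from a difference in effect. The efficacy section plans no table of baseline pain and no outcome rate by baseline level, so a reader could not tell which of the two is being seen.

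**Working it through.** The documents state no sample size in numbers, no target rate and no baseline pain distribution, so there is no planned figure to reproduce. The check has two parts.

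**1. Definitions (no assumptions).** There are 4 × 4 = 16 possible moves from baseline to 2 hours.

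- Relief: moderate to mild, moderate to none, severe to mild, severe to none (4 moves).
- Freedom, by the analysis section: mild to none, moderate to none, severe to none (3 moves).
- Freedom but not relief: mild to none.
- None to none is not a decrease, so it is not freedom under the analysis section.

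Effect on the relief denominator: a child with four qualified treatments, three of them mild at the start, can reach at most 1/4 = 25% relief and so cannot be a responder. A child with two mild starts and two moderate starts, one of which is relieved, scores 1/4 = 25% (non-responder) on all treatments but 1/2 = 50% (responder) on the moderate starts alone.

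**2. Illustration (all inputs assumed).** Let m be the share of mild starts, f1 the freedom rate from mild, f2 the freedom rate from moderate or severe, and r2 the relief rate from moderate or severe.

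- Freedom per treatment = m·f1 + (1 − m)·f2. The shift from a moderate/severe-only rate is m·(f1 − f2).
- Relief per treatment, with mild starts kept in the denominator = (1 − m)·r2.
- Responder rate over n treatments = P(X ≥ n/2), X binomial, with the same rate for every child and independent treatments. For n = 2 this is 1 − (1 − p)²; for n = 4 it is 1 − (1 − p)⁴ − 4p(1 − p)³.

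Freedom, with m = 0.3 and f2 = 0.25. The comparator, moderate/severe only with n held fixed, is 43.8% (n = 2) and 26.2% (n = 4).

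| f1 | Per treatment | Responders, n = 2 | Responders, n = 4 |
|---|---|---|---|
| 0.15 | 0.220 | 39.2% | 21.2% |
| 0.25 | 0.250 | 43.8% | 26.2% |
| 0.40 | 0.295 | 50.3% | 33.9% |
| 0.60 | 0.355 | 58.4% | 44.6% |

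Relief, with r2 = 0.60. The comparator, moderate/severe only at n = 2, is 84.0%.

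| m | Per treatment | Responders, n = 2 |
|---|---|---|
| 0.1 | 0.540 | 78.8% |
| 0.3 | 0.420 | 66.4% |
| 0.5 | 0.300 | 51.0% |

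At m = 0.5 and f1 = 0.40, freedom per treatment is 0.5 × 0.40 + 0.5 × 0.25 = 0.325, above relief at 0.300. The nominally stricter endpoint would then show the higher rate.

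**Cost of restricting to moderate or severe starts.** With four treatments per child and independent starts, the chance of fewer than two moderate or severe starts is m⁴ + 4(1 − m)m³:

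- m = 0.3: 0.0081 + 0.0756 = 0.0837, about 8%.
- m = 0.4: 0.0256 + 0.1536 = 0.1792, about 18%.

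**The case against.** The freedom definition is explicit, and it matches the one for disability. Being pain-free is a clear end state from any starting level, and the plan nowhere promises that freedom sits inside relief. The documents do not say how the earlier adolescent and adult results defined freedom. If those used any starting level, moving the headline to moderate or severe starts would harm the very comparison that the hypothesis needs. The study period also ended in October 2023, so redefining the main endpoint now could be post hoc. These are secondary endpoints in a single-arm study with safety as primary and no test, error rate or margin stated. All of this stands. It argues for keeping the any-pain result as the main one; it does not remove the need to show the severity mix and state the denominators.

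A reader might go further and infer that sessions begun without headache count as pain freedom, because the synopsis sets no baseline condition and the device is cleared "for the acute and/or preventive treatment of migraine". The documents do not support that. The calculation rule requires a decrease, which a session starting at no pain cannot show. It applies to attacks, and the indication studied is acute treatment. The synopsis omits the baseline condition for relief in the same way, so this is an incomplete summary and not a competing rule.

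**Conclusion.** The concern holds as a matter of definition. Mild to none is freedom and never relief, no qualifying rule removes mild starts, and freedom is not nested in relief. If the responder rule is applied as written, mild starts can only lower a child's relief proportion. The freedom rate moves with the mild share whenever freedom rates differ by starting severity.

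It is tempting to conclude that easy attacks inflate the freedom rate. That is plausible, since a mild headache needs only one step to reach none, but the documents do not show it. The shift is upward only if f1 exceeds f2, zero if they are equal and downward otherwise, and its size also depends on m. None of these quantities is given. The range of 21.2% to 44.6% against 26.2% at four treatments shows how sensitive the rate is under assumed inputs; it does not estimate a bias.

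The primary safety endpoint is unaffected. What is at stake is how two secondary efficacy rates can be read, beside each other and against earlier populations.

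**What to change.** 1. Keep freedom from any baseline pain as the main result, label it so, and add to the synopsis endpoint that baseline pain must be at least mild, in line with the analysis section.
2. State the denominator for each pain endpoint. Compute consistent relief only on qualified treatments with moderate or severe baseline pain.
3. Add a supportive row giving consistent freedom on those same moderate or severe starts, so that freedom is nested in relief there, and a separate row for mild starts.
4. Report the distribution of baseline pain over qualified treatments.

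The data are already held, since pain before and after treatment is collected in the app. The change costs a few sentences and two table rows. The restricted rows rest on fewer treatments per child, and children with fewer than two moderate or severe qualified treatments leave them (about 8% or 18% under the assumptions above), so each row should give its own number of children and treatments. If results are already known, the added rows should be labelled post hoc.
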